#### **6.4.    Unscheduled Visits or Telephone Contacts (Visit U01 or T01, etc)**

An unscheduled visit or telephone contact may be performed at any time during the study at the subject's request or as deemed necessary by the site investigator. The date and reason for the unscheduled visit or telephone contact will be recorded in the source documentation. In addition, unscheduled visits will be documented in the database.

### **7.    STUDY ASSESSMENTS**

#### **7.1.    Clinical Assessments**

##### **7.1.1    MDS-UPDRS**

The MDS-UPDRS is a multimodal scale assessing both impairment and disability and is separated into 4 subscales (Parts I-IV). The MDS-UPDRS includes components assessed by the study investigator as well as sections completed by the subject. Every effort should be made to have the same investigator (or coordinator if delegated) perform the ratings for an individual subject throughout the course of the study.

- Part I: This assesses non-motor experiences of daily living and is comprised of two components:
  - ❖ Part IA contains 6 questions that are assessed by the investigator and focuses on complex behaviors.
  - ❖ Part IB contains 7 questions that are part of the Patient Questionnaire completed by the subject.
- Part II: This assesses motor experiences of daily living. There are an additional 13 questions that are also part of the Patient Questionnaire completed by the subject.
- Part III: This assesses the motor signs of PD and is administered by the investigator.
- Part IV: This assesses motor complications, dyskinesias and motor fluctuations using historical and objective information for subjects taking PD medications. The investigator will complete this assessment.

##### **7.1.2    Hoehn and Yahr Stage**

The Hoehn and Yahr is a commonly used system for describing how the symptoms of Parkinson's disease progress. The scale allocates stages from 0 to 5 to indicate the relative level of disability. This scale is included within the MDS-UPDRS and will be completed for all subjects.

- Stage 0: No symptoms.
- Stage 1: Symptoms on one side of the body only.
- Stage 2: Symptoms on both sides of the body. No impairment of balance.
- Stage 3: Balance impairment. Mild to moderate disease. Physically independent.
- Stage 4: Severe disability, but still able to walk or stand unassisted.
- Stage 5: Wheelchair-bound or bedridden unless assisted.

### **7.1.3 Modified Schwab & England Activities of Daily Living**

The Modified Schwab & England Activities of Daily Living (ADL) scale reflects the speed, ease, and independence with which an individual performs daily activities, or personal chores, such as eating, toileting, and dressing. This scale uses a rating scale from 0% to 100%, with 100% representing complete independence in performing daily activities and 0% representing a vegetative, bedridden state.

### **7.1.4 Neuropsychological and Cognitive Assessments**

The Montreal Cognitive Assessment (MoCA): In early Parkinson's disease, when cognitive deficits occur, they are subtle and mild and the patients usually perform in the normal range on the widely used Mini Mental State Examination (MMSE). The Montreal Cognitive Assessment (MoCA) is a rapid screening instrument like the MMSE but was developed to be more sensitive to patients presenting with mild cognitive complaints. It assesses short term and working memory, visuospatial abilities, executive function, attention, concentration, language and orientation. The total score ranges from 0 to 30.

## **7.2. Safety Assessments**

### **7.2.1 Medical History and Neurological Examination**

Medical, smoking, alcohol, and family history, as well as a neurological exam will be captured on all subjects at Baseline.

### **7.2.2 Vital Signs/Weight/Height/Temperature**

Height, weight, sitting pulse rate, sitting blood pressure, and oral temperature will be determined at the Baseline Visit. At Visit 02 pulse rate, blood pressure, and temperature will again be determined. The blood pressure and pulse rate will be determined after 1-3 minutes of quiet sitting.

### **7.2.3 Clinical Laboratory Tests**

Routine clinical laboratory tests will be performed according to the visit schedule. All samples for laboratory analysis must be collected, prepared, labelled, and sent according to the local laboratory's requirement as detailed in the Operations Manual. The total amount of blood needed for the clinical lab tests will be no more than 13 ml.

The coagulation panel (PT/PTT) and platelet counts will be collected and processed at each local lab for analysis at the Baseline Visit. Sites will be provided with supplies from the central lab; however, the sample should be sent to a local lab facility for analysis. Results will be evaluated to determine, in the opinion of the investigator, whether there are any issues that may preclude conduct of the follow-up lumbar puncture. Results should be maintained as part of the subject's study documents; however, they will not be included in the study database.

No more than 40 ml will be drawn at any visit, including both clinical and research blood samples.

### **7.3. Other Assessments**

#### **7.3.1 Biologic Sampling (Blood, Saliva and Urine)**

Blood, saliva, and urine samples will be collected. Blood (about 10-30 ml) will be collected to conduct proteomic, metabolomic and other analyses at each visit. Blood will be obtained (about 8 ml) for the extraction of DNA to conduct sequencing and genomic analyses. Blood will also be obtained (about 7.5 ml) for the extraction of RNA to conduct biochemical analyses. Saliva (about 5 ml) will be collected to conduct biochemical analyses. Additionally, urine (about 15 ml) will be collected to conduct analyte analyses. It is strongly advised that the research blood samples are collected in a fasted state (i.e., minimum of 8 hours since last meal/food intake) to ensure the quality of samples for future analyses. If fasting is not possible, then subjects should be strongly advised to eat a low lipid diet as provided. Subjects are to refrain from eating, drinking or using oral hygiene products for at least one hour prior to saliva collection. A part of the research samples will be sent to a central repository and the rest will be stored locally indefinitely for research purposes. Samples will be made available to researchers to conduct analyses related to PD and other disorders. Subjects will not receive any individual results of analysis or testing conducted on the biologic samples.

#### **7.3.2 Lumbar Puncture**

The lumbar puncture (LP) is performed by the site investigator or another qualified clinician appointed by the investigator. A lumbar puncture for the collection of 15-20 ml of CSF will be conducted for all subjects per the visit schedule unless there is evidence of clinically significant coagulopathy or thrombocytopenia that would interfere with the safe conduct of the procedure. With subject permission, a problematic lumbar puncture may be repeated on the same day or another day and guided by ultrasound or fluoroscopy. Two (2) ml of CSF will be processed at the site's local lab facility (unless the lab is not able to process the CSF within 4 hours) to conduct standard analyses on cell count, protein and glucose levels. Subjects will be closely monitored during the procedure and following the procedure. Subjects will be contacted by phone 7 to 10 days following an LP to assess for any adverse events. A portion of CSF samples will be sent to a central repository and the rest will be stored indefinitely for research purposes. The CSF samples will be made available to researchers to conduct analyses related to PD and other disorders.

## **8. CONCOMITANT MEDICATIONS**

### **8.1. Concomitant Medications**

The medication used is at the discretion of the treating physician. The investigator will document any new medications or changes in medication at each study visit on the Concomitant Medication Log.

**8.1.1 Use of Concomitant Medications**

Concomitant medications, including over-the-counter (OTC), dietary supplements (e.g., herbal remedies) or prescriptions, are permitted during the study period. All concomitant medications reported at the time of the Baseline Visit and for the duration of the subject’s participation should be recorded on the Concomitant Medication Log.

**9. INTERCURRENT ILLNESS**

In the event of an intercurrent illness and at the discretion of the investigator, the subject may be continued in the study. All intercurrent illnesses must be recorded in the eCRF as adverse events if they occur during the period from the LP to the 7-10 day follow-up reporting call.

**10. SUBJECT WITHDRAWALS**

Subjects will be advised in the written informed consent forms that they have the right to withdraw from the study at any time without prejudice, and may be withdrawn at the investigator’s or sponsor’s discretion at any time. A subject should be withdrawn from the study if the investigator considers it to be medically necessary, or if the subject withdraws consent. All reasons for subject withdrawals from the study will be recorded in the source documentation and appropriate eCRF.

**11. SAFETY/ADVERSE EXPERIENCES**

Site investigators and coordinators will be instructed to assess for adverse events from the time the LP is conducted through the telephone follow-up 7 to 10 days following the LP.

Each subject must be carefully monitored for adverse events (AEs). An assessment must be made of the seriousness, intensity, and relationship to the study procedure.

See table below for adverse event monitoring timelines:

Procedure	Assessed from time of procedure		7 to 10 day telephone contact
Lumbar Puncture	X		X

**11.1. Adverse Event Definitions**

**Adverse Events (AE)**

An AE is any undesirable experience occurring to a subject during a clinical trial, whether or not considered related to an investigational product or trial procedures.

Pre-existing conditions (i.e., undesirable experiences, signs or symptoms that begin prior to the Baseline Visit) will be recorded on the medical history CRF page. These conditions will

not be reported as an AE unless they worsen in intensity or frequency during the reporting period defined above.

**Serious Adverse Event (SAE)**

An SAE is an AE that is fatal or life-threatening, or results in hospitalization, prolongation of hospitalization, persistent or significant disability/incapacity, or a congenital anomaly/birth defect. A life-threatening AE is an AE that, in the view of the investigator, places the subject at immediate risk of death from the reaction, as it occurred. Important medical events that may not result in death, be life-threatening, or require hospitalization may be considered an SAE when, based upon appropriate medical judgment, they may jeopardize the subject and may require medical or surgical intervention to prevent one of the outcomes listed in this definition.

Inpatient admission in the absence of a precipitating, study related, clinical adverse event is not subject to immediate reporting. For example:

- Admission for treatment of a pre-existing condition not associated with the development of a new AE
- Social admission (e.g., subject has no place to sleep)
- Protocol-specific admission during a clinical study (e.g., for a procedure required by another study protocol)
- Optional admission not associated with a precipitating clinical adverse event (e.g., for elective cosmetic surgery)

Inpatient admission does not include the following:

- Emergency Room/Accident and Emergency/Casualty Department visits
- Outpatient/same-day/ambulatory procedures
- Observation/short-stay units
- Rehabilitation facilities
- Hospice facilities
- Respite care (e.g., caregiver relief)
- Skilled nursing facilities
- Nursing homes
- Custodial care facilities

**11.2. Recording of Adverse Experiences**

Adverse experiences, whether observed by the investigator, elicited from or volunteered by the subject, should be recorded on the Adverse Event Log. This will include a brief description of the experience, the date of onset, the date of resolution, the severity, and seriousness and whether the event was related to participation in the research study.

Any AE ongoing at the final 7 to 10 day reporting telephone visit should be followed until resolution or stabilization, but not more than 30 days from LP.

### **11.3. Responsibilities for Reporting Serious Adverse Experiences**

- The investigator should notify the CTCC Project Manager by telephone within 24 hours of his/her becoming aware of the occurrence of a serious adverse experience.
- Upon completion of the telephone report, the CTCC Project Manager will enter the appropriate subject information into the Incident Module.
- The following information should be supplied if available at the time of the telephone call: study number, site number, subject number, subject age and gender, date of onset of event, event description, whether event required treatment, death and autopsy report, an identification of which criteria for a serious experience have been met, the investigator's current opinion of the relationship between the event and study participation.
- The investigator will comply with his/her local Institutional Review Board (IRB) regarding the reporting of adverse experiences.

## **12. REPORTABLE EVENTS**

The following incidents will be considered reportable events and will be reported to the CTCC within 24 hours of the event, or the site investigator's knowledge of the event.

- Change of clinical diagnosis
- Participation in any other clinical trial or study
- Premature withdrawal (e.g. withdrawal of consent)
- SAE
- Death

## **13. REFERRALS**

If a research assessment or lab result reveals a clinically significant abnormality the subject should be informed of this result and instructed to follow up with his or her primary care physician. Should there be a safety concern warranting a referral for medical or psychiatric follow-up, the investigator should provide the subject with the appropriate referral as necessary.

## **14. POTENTIAL RISKS**

### **14.1. Blood Sampling**

Risks associated with venous blood draw include pain and bruising at the site where the blood is taken. Sometimes people can feel lightheaded or even faint after having blood drawn.

### **14.2. Lumbar Puncture**

The most common risks of a lumbar puncture are pain at the site and a temporary headache usually due to a small amount of CSF leakage around the needle insertion site. Lying down for a few hours after the test can make a headache less likely to occur. There is a slight risk

of infection because the needle breaks the skin's surface, providing a possible portal of entry for bacteria. A temporary numbness to the legs or lower back pain may be experienced. There is a small risk of bleeding in the spinal canal. Subjects will have blood drawn at Baseline to test for coagulopathies.

## **15. STATISTICAL ANALYSIS**

### **15.1. Sample Size Determination**

*This study is a prospective study without a predefined assay, and therefore does not have power calculation. However, we considered sample size based on three examples:*

1. The sample size was initially calculated using Khoo's miRNA data using 50% quartile of variance to detect 2.5 fold changes with 80% power at  $\alpha=0.0025$ .
2. Based on [name] lab's preliminary data on the ratio of oxidized DJ-1 to total DJ-1 in RBC in 12 subjects, 120 PD subjects will provide 85% power to detect 33% difference at  $\alpha=0.05$ .
3. We also surveyed other biomarker studies involving PD diagnosis. The studies with the largest number of subjects included about 120 PD subjects of various stages of PD and were able to detect differences between PD and controls for various markers.

### **15.2. Treatment Failures, Non-Compliance, and Withdrawals**

Those who have abnormal platelet counts ( $<50,000/\text{ul}$  or by local lab standard), PT (below or above 11.8 – 14.5 or local lab normal values), PTT (below or above 24.0 – 34.0 or local lab normal values), or INR values (below or above 0.9 – 1.1 or local lab normal values) will be excluded from LP, but undergo blood draw and other activities in the second visit. Those whose spinal tap is unsuccessful in producing CSF will be included in the study with only clinical data and blood samples.

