## **2. STUDY OBJECTIVE**

### **2.1. Primary Objective and Specific Aims**

The primary objective of the study is to collect biospecimens from 120 PD and 120 healthy controls with well defined clinical characteristics for future biomarker assays.

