**6.3. Final Visit/Visit 02(FNL/V02)**

This visit should occur within 2 weeks of Baseline/Visit 01 if possible or soon thereafter if necessary. The results of CBC, platelets, and PT/PTT are checked to make sure that normal values are documented before LP. If abnormal, Visit 02 can occur for other activities without LP.

**Blood draw, saliva and urine collections, LP, and MDS-UPDRS part 3 motor examine should occur early in the morning before any PD medication dose. Preferably subjects**

**should be fasting. If fasting is not feasible, a low fat diet is recommended. Subjects are to refrain from eating, drinking or using oral hygiene products for at least one hour prior to saliva collection.**

With subject permission, samples determined to be unusable may be recollected at a later date.

Activity and Assessments	PD	Control
Vital Signs: Measure temperature, sitting heart rate, and sitting blood pressure	+	+
Concomitant Medication: Review and record concomitant medications	+	+
Movement Disorder Society Unified Parkinson Disease Rating Scale (MDS-UPDRS)	+ part 3 motor portion only	N/A
Hoehn and Yahr Stage	+	N/A
Blood draw: 3 × 2.5 ml PAXgene™ 3 × 10 ml plasma EDTA purple top	+	+
Saliva collection: About 5 ml	+	+
Urine collection: About 15 ml	+	+
Lumbar Puncture: Collection of cerebral spinal fluid	+	+
Adverse Event: Review and record adverse events from LP through 7-10 day follow-up call	+	+

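### Section 15.2, read literally, leaves out saliva and urine for subjects whose tap yields no CSF, against 6.3, 7.3.1 and its own rule for laboratory-excluded subjects

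*Protocol*

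**What the plan says.** Section 15.2 of the protocol covers two ways in which a subject can end up without CSF.

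- **Laboratory values rule out the puncture.** These subjects "will be excluded from LP, but undergo blood draw and other activities in the second visit". Section 6.3 agrees: "If abnormal, Visit 02 can occur for other activities without LP".
- **The puncture is attempted but yields nothing.** "Those whose spinal tap is unsuccessful in producing CSF will be included in the study with only clinical data and blood samples".

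On saliva and urine, section 6.3 places everything in one session: "Blood draw, saliva and urine collections, LP, and MDS-UPDRS part 3 motor examine should occur early in the morning before any PD medication dose". Its activity table marks saliva (about 5 ml) and urine (about 15 ml) for both cohorts, and both schedules of activities list them at V02. Section 7.3.1 treats them as research specimens: "Blood, saliva, and urine samples will be collected". None of these places makes collection depend on the result of the puncture.

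The primary objective in section 2.1 is to "collect biospecimens from 120 PD and 120 healthy controls with well defined clinical characteristics". Section 7.3.2 allows a second attempt: "With subject permission, a problematic lumbar puncture may be repeated on the same day or another day and guided by ultrasound or fluoroscopy".

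**The concern.** The word 'only' in 15.2 is exclusive. It names clinical data and blood, and so leaves out two specimen types that have nothing to do with the spinal tap. Saliva and urine are as valid after a failed tap as after a successful one.

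The result is also lopsided. A subject who never has a puncture, because of laboratory values, contributes blood, saliva and urine. A subject who undergoes the puncture without yield contributes blood alone. The protocol offers no reason for this.

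The study's product is the specimen bank, so a sentence that defines what a subject contributes is a working rule. A site or repository that followed 15.2 to the letter would either not collect these samples or not include them. Section 6.3 does not fix the order of procedures within the visit, so either could happen.

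**Working it through.** The plan has no figure of its own on this point to reproduce. The check is a comparison of passages, followed by a simple count.

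**Step 1. What each kind of subject contributes at Visit 02, as written**

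| Subject | Blood | Saliva | Urine | CSF | Source |
|---|---|---|---|---|---|
| Tap successful | yes | yes | yes | yes | 6.3, 7.3.1, 7.3.2, schedules |
| No tap, abnormal laboratory values | yes | yes (other activities) | yes (other activities) | no | 15.2 first sentence, 6.3 |
| Tap attempted, no CSF | yes | not named; 'only' excludes it | not named; 'only' excludes it | no | 15.2 second sentence |

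The last two rows have the same CSF status but different saliva and urine entries. The third row also disagrees with the 6.3 table and the schedules, which set no condition on the tap.

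**Step 2. How many sets are exposed**

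Inputs:
- Planned subjects: 120 PD + 120 controls = 240 (synopsis, 2.1; 4.1 says approximately).
- Tap failure rate f: not given in the protocol. Assumed range: 5% to 15%.

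Formula: sets affected = 240 × f, if every failed tap is handled by the literal rule and none is rescued by a repeat.

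- f = 5%: 240 × 0.05 = 12 sets (6 per group if failures are evenly split).
- f = 10%: 240 × 0.10 = 24 sets (12 per group).
- f = 15%: 240 × 0.15 = 36 sets (18 per group).

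These are upper figures for each assumed rate. If a share r of failed taps succeeds on repeat under 7.3.2, the count becomes 240 × f × (1 − r). The protocol gives no value for r.

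**The case against.** The best defence is that 15.2 is loose shorthand for 'without CSF'. Section 6.3 marks saliva and urine for all subjects without condition, section 7.3.1 has research samples kept indefinitely, and a sensible site would collect and ship them anyway. Section 16.1 sends procedures not described in the protocol to an Operations Manual that is not at hand and may settle the matter. This is a fair reading of intent and it limits how serious the point is. It does not remove the conflict, because 15.2 does describe the case and describes it differently from 6.3.

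A reader might infer more than the text supports:

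- **That specimens are discarded.** Nowhere does the protocol say that saliva or urine is destroyed or withheld after a failed tap. What can be said is that 15.2 omits them.
- **That subjects without CSF count toward 120 + 120.** Section 15.2 says they are included in the study. The protocol does not say whether they fill one of the 120 places or are replaced. Even if they do, nothing is contradicted, because the objective is worded as biospecimens and not as CSF.
- **That users of the CSF bank are promised 120 per group, so CSF precision is overstated.** The protocol makes no such promise and states no CSF precision. Section 15.1 disclaims a power calculation. Its 85% example concerns a ratio measured in red blood cells, which a failed tap does not change.
- **That example 3 sets a CSF requirement.** It observes that "The studies with the largest number of subjects included about 120 PD subjects of various stages of PD". The two references carry CSF titles, but the example is a survey of earlier study sizes with no effect size or power attached, so no CSF detectable difference can be derived from it.

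The range of 5% to 15% is an assumption, and the repeat puncture in 7.3.2 lowers the final number. Both qualifications stand.

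**Conclusion.** The point holds as an internal inconsistency. Section 15.2 disagrees with 6.3, 7.3.1, the schedules and its own preceding sentence on what a subject without CSF contributes. Followed literally, it would leave valid saliva and urine out of a study whose primary objective is to collect biospecimens.

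The size is 12 to 36 of 240 sets. That figure rests on an assumed 5% to 15% failure rate, on literal application of the rule and on no rescue by repeat puncture; the true number could be smaller, and is zero if sites follow 6.3 instead. No stated calculation in the protocol is wrong because of this, and no conclusion about CSF power follows. It is still worth correcting, because the change costs almost nothing and a pre-medication morning sample that is not taken may not be recoverable later.

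**What to change.** Reconcile 15.2 with 6.3 and 7.3.1. The second sentence of 15.2 should say that a subject whose tap yields no CSF stays in the study with clinical data and with blood, saliva and urine samples. This matches the rule already applied to subjects barred from the puncture by laboratory values.

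As an optional clarification, and not the correction of an error, state in 2.1 or 4.1 whether 120 per group means enrolled subjects or subjects with CSF, and whether subjects without CSF are replaced.

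The cost is one clause in a protocol amendment, plus one sentence if the clarification is adopted. The clause needs no extra subjects, visits or procedures, since saliva and urine are already scheduled for everyone.
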